## 9.2. Clinical Laboratory Evaluations

Non-PK/PD blood and urine samples will be obtained per the schedule of assessments in Table 2.

Laboratory test results and change from baseline will be summarized by panel, parameter, time point, and treatment. Laboratory results, including lab normal ranges, will be listed by treatment category, subject, parameter, and time point.

For continuous laboratory data that are reported using "<" or " $\leq$ ", a value of the number presented less one level of precision will be used for tables and figures. If the resulting value is equal to zero, the value will be adjusted by an additional level of precision. Similarly, ">" or " $\geq$ " will result in adding one at the level of precision for use in tables and figures. Actual results will be presented in the data listings. Table 6 provides example imputations.

Reported Value	Imputed Values
< 23	22
< 2.3	2.2
< 2	1
< 1	0.9*

Table 6:Example Imputation of Inequalities

< 0.23	0.22
< 0.1	0.09*
< 0.10	0.09
< 0.0200	0.0199
> 1.030	1.031
> 8	9

\*value precision adjusted

Hemoglobin and other transfusion-impacted parameters will be summarized using the rules for transfusion-impacted periods as described in Section 5.7.13.

Select lab parameters including but not limited to serum creatinine and urine albumin/creatinine ratio will be plotted versus time from Day 1 to last visit.

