## 5.7.3. Change from Baseline

Change from baseline is calculated as (post-baseline result – baseline result). Percent change from baseline is calculated as (100 x change from baseline/baseline result). If either the baseline or the post-baseline result is missing, the change from baseline and percent change from baseline are set to missing as well. If the baseline result is 0, then the percent change from baseline is set to missing.

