## 5.7.13.1. Transfusion-impacted Period for South Africa

The algorithm as defined below aims to exclude transfusion impacted lab measurements when possible, and acts to select local lab measurements over central lab measurements (for South Africa subjects) or central lab measurements over local lab measurements (for subjects outside of South Africa), when possible. This is due to a lack of reliable data obtained from the central lab in South Africa.

For South African sites, the algorithm for determining which values should be used in effectiveness analysis are as follows:

The Hb value to use for a particular visit is provided below. The first item matching the description in the list should be used.

- 1. Local lab value for Hb at the visit of interest closest to the target day.
  - a. If multiple results are equidistant from the target, use the latest.
  - b. If multiple records exist on the same day, find the median of the results on that day (for grading, set to the most frequent grade or worst grade if two grade have the same frequency).
- 2. Central lab value for Hb at the visit of interest closest to the target day.
  - a. If multiple results are equidistant from the target, use the latest.
  - b. If multiple records exist on the same day, find the median of the results on that day (for grading, set to the most frequent grade or worst grade if two grade have the same frequency).

If the value at the visit of interest was taken during a transfusion-impacted period:

- 3. Local lab pre-transfusion value that itself was not within 14 days after the subject received a pRBC or whole blood transfusion.
  - a. If multiple results are equidistant from the target, use the latest.
  - b. If multiple records exist on the same day, find the median of the results on that day (for grading, set to the most frequent grade or worst grade if two grade have the same frequency).
- 4. Central lab pre-transfusion value that itself was not within 14 days after the subject received a pRBC or whole blood transfusion.
  - a. If multiple results are equidistant from the target, use the latest.
  - b. If multiple records exist on the same day, find the median of the results on that day (for grading, set to the most frequent grade or worst grade if two grade have the same frequency).

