#### **10.1.2.** Clinical Measurements of PNH

Continuous clinical measurements of PNH (LDH, hemoglobin, haptoglobin levels, absolute reticulocyte count, AST, total bilirubin, and direct bilirubin) will be summarized by summary statistics including change from baseline and percent change from baseline, by treatment category and study visit. Note that LDH, hemoglobin, haptoglobin, and absolute reticulocyte count that occur within a transfusion-impacted period will not be included in summaries but will be presented in respective listings. Categorical clinical measurements of PNH (number of blood transfusions, incidence of major thromboses) will be summarized with counts and percentages by treatment category (see Section 12.3 for a list of thrombosis events). Incidence of breakthrough hemolysis will be analyzed by the sponsor.

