## 11.2. Pharmacodynamic Analyses

In this study, PD assessments include PNH clone size (RBC and WBC), Factor Bb, serum AP activity as assessed by AP Wieslab, and additional exploratory assays.

Descriptive summaries of the above assessments including change from baseline will be presented by treatment category, dose regimen, and study visit. AP Wieslab (and other similar assays, if applicable) will be reported only as percent of baseline, not as actual value or percent change from baseline. Data values will be listed.

If PD assessments are reported with inequalities ( $<, \leq, >, \text{ or } \ge$ ), the same conventions used for laboratory values as described in Section 9.2 will be used.

Any further analysis of PD data including the relationship to PK concentrations will be performed under a separate analysis plan.

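### The SAP's substitution for `<` and `>` laboratory results depends on printed decimals, so it can create or distort changes from baseline, chiefly for haptoglobin

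*SAP*

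**What the plan says.** SAP 9.2 sets the rule for continuous results reported with `<` or `≤`: "a value of the number presented less one level of precision will be used for tables and figures". There is one exception: "If the resulting value is equal to zero, the value will be adjusted by an additional level of precision". Results with `>` or `≥` have one unit of the last printed digit added. "Table 6 provides example imputations", ten in all. The raw values are kept: "Actual results will be presented in the data listings".

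Three parts of the plan bring the rule into efficacy-type summaries.

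- SAP 10.1.2 summarises LDH, hemoglobin, haptoglobin, reticulocytes and others "including change from baseline and percent change from baseline, by treatment category and study visit". SAP 5.7.3 defines the measure: "Percent change from baseline is calculated as (100 x change from baseline/baseline result"). The baseline value is the denominator.
- SAP 11.2 says that for PD results with inequalities "the same conventions used for laboratory values as described in Section 9.2 will be used". PD assays are summarised as values and change from baseline, except that AP Wieslab is shown only as percent of baseline.
- SAP 5.6 and 5.7.13 choose between laboratories. For South African subjects the algorithm "acts to select local lab measurements over central lab measurements"; elsewhere the order is reversed. In both cases the other laboratory is the fallback. Haptoglobin follows this algorithm, with a shorter transfusion period. Protocol 13.6 also lets investigators use a local laboratory for logistical reasons.

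**The concern.** A substitution for an undetectable result should depend on the assay and its limit. This one depends on the number of decimals on the report. In Table 6, `< 2` becomes 1, which is 50% of the limit, while `< 0.0200` becomes 0.0199, which is 99.5% of it.

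This can reach the tables in two ways.

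- **Within a subject.** If baseline and a later visit come from laboratories that print different decimals, two undetectable results can appear as a rise or a fall.
- **Between subjects.** South African subjects (local laboratory preferred) and all others (central preferred) share the same summaries. If formats differ, identical true changes from an undetectable baseline enter as different percent changes.

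Haptoglobin is a secondary endpoint. A mean percent change with a very small imputed denominator is sensitive to this. If more than half of the baselines are below the limit, the median is affected too.

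**Working it through.** **Inputs.** The rule, the zero exception and the examples come from SAP 9.2 and Table 6. The percent-change formula comes from SAP 5.7.3. The documents state no detection limit or print format for haptoglobin or any PD assay, so limits other than those in Table 6 are assumptions, shown as a range.

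**Reproducing the plan's figures.** Let u be one unit of the last printed digit. A `<` result becomes limit - u; if that is zero, limit - u/10. A `>` result becomes limit + u. This returns all ten Table 6 rows exactly: 22, 2.2, 1, 0.9, 0.22, 0.09, 0.09, 0.0199, 1.031 and 9.

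**Same limit, one more decimal.** Write the limit as k units of the last digit in the coarser format, with k ≥ 2. The coarse value is (k - 1)u and the finer value is (k - 0.1)u, so the apparent ratio is (k - 0.1)/(k - 1).

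| First result, then second | Imputed values | Change | Reverse order |
|---|---|---|---|
| `< 0.2`, `< 0.20` | 0.1, 0.19 | +90.0% | -47.4% |
| `< 0.3`, `< 0.30` | 0.2, 0.29 | +45.0% | -31.0% |
| `< 5`, `< 5.0` | 4, 4.9 | +22.5% | -18.4% |
| `< 10`, `< 10.0` | 9, 9.9 | +10.0% | -9.1% |
| `< 23`, `< 23.0` | 22, 22.9 | +4.1% | -3.9% |
| `< 0.1`, `< 0.10` | 0.09, 0.09 | 0% | 0% |
| any limit, same format | equal | 0% | 0% |

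With further decimals the ratio approaches k/(k - 1), which is at most 2. For example, `< 0.02` then `< 0.0200` gives 0.01 and 0.0199: +99.0%, reverse -49.7%.

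**Rise from an undetectable baseline to 1.0.** From `< 0.2`: (1.0 - 0.1)/0.1 = +900%. From `< 0.20`: (1.0 - 0.19)/0.19 = +426%. No switch within a subject is needed; two subjects with different laboratories suffice.

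**Results above a limit.** `> 8` gives 9 and `> 8.0` gives 8.1. The change is (8.1 - 9)/9 = -10.0%, reverse +11.1%.

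**Effect on a group mean.** Suppose a share s of subjects is undetectable at both visits and switches from `< 0.2` to `< 0.20`. The mean percent change moves by s × 90 points: 4.5 points at s = 5%, 9 at 10%, 18 at 20%. The shares are assumptions.

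**Route for haptoglobin.** Under SAP 5.6 its baseline is derived as for hemoglobin. Averaging across laboratories is barred there, except in the last-resort baseline, which averages all central and local pre-treatment values. Nothing requires baseline and later values to come from the same laboratory or format.

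**Route for PD assays.** The documents describe no second laboratory for Factor Bb or AP Wieslab. What remains is the reference value: a below-limit baseline is set by print format, and change from baseline (or percent of baseline for AP Wieslab) is measured against it.

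**The case against.** The strongest reply is that the necessary condition is not in the documents. They do not say that formats differ, and with a constant format the artefact between two undetectable results is exactly zero. The laboratory rules mostly limit mixing: each subject has a preferred laboratory, and the other is a fallback. Table 6's only pair with the same limit in two formats, `< 0.1` and `< 0.10`, agrees at 0.09. The largest figures need a limit only two units above zero in the last digit.

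All of this stands, and it rules out some stronger readings. A reader might infer that the rule does produce false changes, or that the SAP routinely mixes laboratories within subjects. The documents support only that it can, through fallback and pooling. A reader might also infer false percent changes in the PD assays. That is not supported: no route to a format switch is shown, and SAP 11.2 plans change from baseline, with AP Wieslab as percent of baseline only.

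The stakes are also limited. The primary endpoint is safety, the SAP puts estimation above testing, medians accompany means, raw results stay in the listings, and the response categories in SAP Table 5 do not use haptoglobin. None of this defends the rule itself, which has no assay-based rationale.

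**Conclusion.** The concern holds in a conditional form. The rule in SAP 9.2 depends on format, for both `<` and `>` results, and the haptoglobin and PD summaries inherit it. For haptoglobin there is a documented route by which it can create or distort changes and percent changes. For PD assays the point is confined to an arbitrary baseline value.

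On assumed limits, the apparent change between two undetectable results at the same limit runs from 0% to just under two-fold. It is about 4% where the limit is 23 units of the last digit, and 90% or more where it is 2. How often this would occur cannot be determined, because limits, formats and below-limit frequencies are not given.

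No test or decision rule turns on it. It is worth correcting because a stated rule can put artefacts into a secondary endpoint's tables and the correction is nearly free.

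**What to change.** In SAP 9.2, and through it 11.2:

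1. Use one substitution value per assay and limit that does not depend on printed decimals, for example a fixed fraction of the limit for `<` and the limit itself for `>`.
2. Set the change between two below-limit results to zero. This also covers laboratories with different limits, which item 1 alone does not.
3. For haptoglobin and the PD assays, report the number and percentage below the limit at each visit, with medians.
4. Flag percent changes and percent-of-baseline values whose baseline is below the limit, and summarise them separately from the means.

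Item 4 is needed because item 1 makes the denominator consistent, not correct. Half of 0.2 is 0.1, so a rise to 1.0 still reads +900%. Items 3 and 4 belong together: means restricted to measurable baselines are selective, so they should supplement the counts and medians, not replace them.

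The cost is SAP wording and one extra derivation. Some mean percent changes will rest on fewer subjects, selectively those with a measurable baseline.

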## 9.2.1. Analysis of Abnormal Laboratory Values

Laboratory abnormalities will be graded according to DMID Adult Toxicity Table (draft version November 2007, see Protocol Appendix 1), with the exception of creatinine clearance and glomerular filtration rate, which will be graded using the National Cancer Institute (NCI) Common Terminology Criteria for Adverse Events (CTCAE) version 4.03.

Any graded abnormality that occurs following the initiation of study drug and represents at least 1-grade increase from the baseline assessment is defined as treatment emergent. The number and percentage of subjects who experience treatment-emergent graded toxicities will be summarized by panel, parameter, time point, and treatment category. Laboratory toxicity shifts from baseline to worst post-baseline grade will be summarized by panel, parameter, toxicity grade, and treatment.

#### 9.2.2. Liver Enzymes

The number and percentage of subjects having elevations in liver enzyme abnormalities (alanine aminotransferase [ALT] or aspartate aminotransferase [AST], or bilirubin) in relation to fold above the ULN will be summarized according to the FDA's Premarketing Clinical Evaluation on Drug-Induced Liver Injury Guidance for Industry (DHHS 2009).

Both fold change from ULN and fold change from baseline will be summarized by visit for ALT, ALP, AST, and bilirubin.

The following categories of abnormal hepatic laboratory values will be evaluated for any occurrence among all post-baseline assessments (where "and" indicates elevations occurring at the same visit). Treatment-emergent elevations will also be summarized. Within each treatment group and laboratory parameter grouping, a subject may be counted once per elevation criteria using the worst-case result. That is, a subject with a worst-case ALT elevation >3 × ULN for a given treatment group would be counted once in the ALT > 1.5 × ULN category and once in the ALT > 3 × ULN category, regardless of how many ALT elevations the subject had that met the > 3 × ULN and > 1.5 × ULN elevation criteria.

- ALT or AST and total bilirubin
  - ALT >  $3 \times$  ULN and bilirubin >  $1.5 \times$  ULN
  - ALT > 3  $\times$  ULN and bilirubin > 2  $\times$  ULN
  - AST >  $3 \times$  ULN and bilirubin >  $1.5 \times$  ULN
  - AST >  $3 \times$  ULN and bilirubin >  $2 \times$  ULN
  - (ALT > 3  $\times$  ULN or AST > 3  $\times$  ULN) and bilirubin > 1.5  $\times$  ULN
  - (ALT > 3  $\times$  ULN or AST > 3  $\times$  ULN) and bilirubin > 2  $\times$  ULN
- AST > 1.5, 3, 5, 10, or 20 × ULN
- ALT > 1.5, 3, 5, 10, or 20 × ULN
- Total bilirubin  $> 1, 1.5, \text{ or } 2 \times \text{ULN}$
- ALP >  $1.5 \times ULN$

Profiles of hemoglobin, liver enzymes (ALT, ALP, AST) and bilirubin over time will be graphically displayed for subjects with any Grade 3 or 4 abnormality in ALT, ALP, AST, or total bilirubin. In addition, a listing of all liver function test (ALT, AST, bilirubin, ALP) results for subjects experiencing a treatment-emergent Grade 3 or 4 liver function test will be provided.

In addition, a Hy's law plot, a shift plot showing liver safety panel tests over time (baseline vs. on-study), and distribution plots of ALT, AST, ALP, bilirubin, cholesterol, and triglycerides over time will be produced using the format recommended by the FDA/Industry/Academia Safety Graphics working group (https://www.ctspedia.org/do/view/CTSpedia/StatGraphHome). The plots to be included are the scatter plot of maximum transaminase versus maximum bilirubin, the liver test safety panel over time, and the distribution of ALT by time and treatment. Distribution plots for AST, ALP, bilirubin, cholesterol, and triglycerides will use the same format as is used for ALT.

## 9.3. Bedside ECGs

Bedside ECGs are obtained as scheduled in Table 2.

Descriptive summaries of bedside ECG parameters (PR, QRS, QT, RR, and QTcF) and change from baseline will be presented by parameter, time point, and treatment category. ECG interpretation (normal, abnormal, abnormal clinically significant) will be presented by time point and treatment including "worst post baseline" (defined as Abnormal if ever Abnormal post-baseline, and otherwise Normal if always Normal post-baseline).

The number and percentage of subjects with  $QTcF \le 450$ , > 450 to  $\le 480$ , > 480 to  $\le 500$ , and > 500 msec; or changes of  $\le 30$ , > 30 to  $\le 60$ , or > 60 msec will be summarized by treatment category and visit along with worst post-baseline result. Unscheduled ECG results will be included in this summary table.

ECG results will be listed by treatment category, subject, parameter, and time point.

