Safety endpoints will be summarized and will include the proportion of subjects: with TEAEs; who discontinue due to a TEAE; who receive a reduced dose due to tolerability issues; who experience a treatment-emergent serious adverse event (SAE); who experience a Grade 3 or 4 TEAE; who experience a treatment-emergent, treatment-related adverse event (AE) consistent with a drug rash (eg, rash, maculo-papular exanthem, papular rash); and who experience Grade 3 or 4 laboratory abnormalities.

AEs will be mapped to a Medical Dictionary for Regulatory Activities (MedDRA) preferred term and system organ classification. The occurrence of TEAEs will be summarized using MedDRA preferred terms, system organ classifications, and severity. In addition to severity, AEs and SAEs will also be summarized based on Investigator assessment of relationship to study drug.

Time to dose reduction, time to discontinuation due to a TEAE, and time to development of drug-related rash will be estimated using the Kaplan-Meier method. For those with a drug-related rash, clinical and laboratory findings will be summarized as will the proportion of subjects who successfully continue therapy following onset of rash.

Descriptive statistics for vital signs, weight, and clinical laboratory results will be presented by study visit. Laboratory abnormalities will be graded according to the Division of Microbiology and Infectious Diseases (DMID) Adult Toxicity Table. The number and percentage of subjects experiencing treatment-emergent graded toxicities will be summarized.

Laboratory toxicity shifts from baseline to the worst post-baseline value as well as the last visit will be summarized. The number and percentage of subjects having elevations in ALT, AST, or bilirubin abnormalities in relation to fold above ULN will be summarized according to the United States Food and Drug Administration's Premarketing Clinical Evaluation on Drug-Induced Liver Injury Guidance for Industry.

Clinically significant abnormal ECG findings will be summarized by study visit. Changes from baseline in ECG parameters will also be summarized by study visit. The number and proportion of subjects with clinically important absolute and change-from-baseline thresholds in QTcF will be summarized.

Analysis of Clinical Measurements of PNH

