14.3.5. Analysis of Safety Variables

Safety endpoints that will be summarized, at a minimum, include the proportion of subjects 1) with TEAEs; 2) who discontinue BCX9930 due to TEAEs; 3) with treatment-emergent SAEs; 4) with treatment-emergent Grade 3 or 4 AEs; and 5) with treatment-emergent Grade 3 or 4 laboratory abnormalities. In addition, the proportion of subjects who received a reduced dose due to tolerability issues at the full dose will be summarized.

Time to dose reduction, time to discontinuation due to a TEAE, and time to development of drug-related rash will be estimated using the Kaplan-Meier method. For those with a drug-related rash, clinical and laboratory findings will be summarized and the proportion of subjects who successfully continued therapy following onset of rash.

AEs will be mapped to a Medical Dictionary for Regulatory Activities (MedDRA) preferred term and system organ class (SOC). The occurrence of TEAEs will be summarized using MedDRA preferred terms, SOCs, and severity. Separate summaries of TEAEs, treatment-emergent SAEs, AEs considered related to study drug, and AEs leading to study drug interruption will be generated. All AEs will be listed for individual subjects showing both verbatim and preferred terms.

Descriptive summaries for vital signs, weight, bedside ECG parameters, and clinical laboratory results will be presented. Laboratory abnormalities will be graded according to the DMID Adult Toxicity Table (Publish Date: Draft, November 2007; Appendix 1).

Any graded abnormality that occurs following the initiation of study drug and represents at least 1-grade increase from the baseline assessment is defined as treatment emergent. The number and percentage of subjects experiencing treatment-emergent graded toxicities will be summarized. Laboratory toxicity shifts from baseline to worst post-baseline assessments will be summarized.

The number and percentage of subjects having elevations in liver enzyme abnormalities (ALT, AST, or bilirubin) in relation to fold above ULN will be summarized according to the Premarketing Clinical Evaluation on Drug-Induced Liver Injury Guidance for Industry.

Clinically significant abnormal morphological ECG findings will be summarized.

The change from baseline in QTcF will be determined by routine ECGs. At each time point ECGs are analyzed, an individual subject's change from baseline will be calculated as:

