## **3.2.** Study Endpoint(s)

#### **3.2.1. Primary Endpoints**

• Measurement of safety and tolerability by subject incidence of graded TEAEs, laboratory abnormalities, changes to vital signs, ECG results, and physical examination findings.

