## 3.5. Number of Subjects

No sample size calculations were conducted for this open-label, long-term safety study. Approximately 200 subjects will be enrolled. Subjects will be eligible to receive BCX9930 for up to 144 weeks or until the Sponsor discontinues development of the product; whichever comes first. Both males and females will be enrolled. As reproductive toxicology studies have not yet been conducted, women of childbearing potential may be enrolled in this trial only if they meet and maintain strict contraceptive and pregnancy test requirements as listed in this protocol.

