i Full physical examinations will be performed at screening and baseline; symptom-directed physical examinations will be performed at all post-baseline visits.

j All ECGs during the study will be single assessments. ECGs will be conducted every 12 weeks up to Week 96 (ie, Weeks 12, 24, 36, 48, 60, 72, 84, and 96) and every 24 weeks thereafter (ie, Weeks 120 and 144) during the treatment period.

k For women of childbearing potential, a serum pregnancy test will be administered at screening; urine pregnancy tests will be assessed at all subsequent visits. Starting at Week 100, women of childbearing potential will start performing urine pregnancy tests at home every 4 weeks (i.e., in between clinic visits). The results will be recorded by the site. If the urine pregnancy test is positive, the subject should contact the site immediately.

FSH will be measured at screening for any woman post-menopausal  $\leq 2$  years (this may be omitted if menopausal status was demonstrated with elevated FSH in the prior study). For women who do not undergo a screening visit, FSH may be assessed at baseline. In this case, the subject must have a negative urine pregnancy test at baseline prior to receiving study drug.

m Cholesterol and triglycerides will be measured every 12 weeks up to Week 96 (ie, Weeks 36, 48, 60, 72, 84, and 96) and every 24 weeks thereafter (ie, Weeks 120 and 144).

n Urine microscopy will be performed on urine collected at investigative site visits (and, where possible, at remote visits where the lab has appropriate on-site testing capability). Urine microscopy should be performed using the site's local laboratory (assuming appropriate on-site testing capability exists) in lieu of the central laboratory.

o Weeks 48, 96, and 144 only.

p Only limited hematology and clinical chemistry parameters measured as per Protocol Section 11.3.5 and Protocol Section 11.3.6.

q Urine will be collected at investigative site visits (ie, excluding remote visits) and aliquots frozen for possible future analysis of urine biomarkers.

r Completed at all treatment visits through Week 96 only.

## 27 of 64

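### The SAP's worst post-baseline ECG row has no clinically significant level, so no planned table counts the subjects who ever had such an interpretation.

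*SAP*

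**What the plan says.** SAP 9.3 (Bedside ECGs) classifies each ECG as normal, abnormal, or abnormal clinically significant, and presents this by time point and treatment. To the time points it adds a 'worst post baseline' entry, "defined as Abnormal if ever Abnormal post-baseline, and otherwise Normal if always Normal post-baseline". The same section summarizes QTcF in four absolute and three change categories by visit, together with a worst post-baseline result, and says that unscheduled ECGs are included in that table.

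The protocol asks for clinically significant ECG findings in two places. The synopsis says "Clinically significant abnormal ECG findings will be summarized by study visit". Section 14.3.5 says "Clinically significant abnormal morphological ECG findings will be summarized", with no mention of visits.

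The primary endpoint (SAP 3.2.1, matching Protocol 6.3) is "Measurement of safety and tolerability by subject incidence of graded TEAEs, laboratory abnormalities, changes to vital signs, ECG results, and physical examination findings".

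In the list of displays (SAP 12.1, Table 7), ECG interpretation has one table, 14.3.5.2, which is by visit. QTcF categories are in Table 14.3.5.3, and individual ECG results are in Listing 16.2.14.

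**The concern.** The worst post-baseline entry is the only planned summary of ECG interpretation that counts each subject once over the whole study, and it has no place for the clinically significant level. A subject with one abnormal ECG of no clinical significance and a subject with a clinically significant one fall in the same cell.

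At stake is one number that a reader of a long-term safety study would expect: how many subjects ever had a post-baseline ECG judged abnormal and clinically significant. The primary endpoint is worded as subject incidence with ECG results among its components, so this is the natural subject-level figure for ECG interpretation.

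The wording also leaves a coding gap. If 'Abnormal' means exactly the middle level, a subject whose ECGs are only normal or abnormal clinically significant is neither ever Abnormal nor always Normal, and the rule does not classify that subject.

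**Working it through.** There is no plan figure to reproduce. SAP 3.5 says that no sample size calculation was done, and neither document gives an ECG abnormality rate. The check is of the rule itself, with two illustrations.

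**1. Apply the rule to possible subject histories.**
- All ECGs normal: Normal.
- Normal and abnormal: Abnormal.
- Abnormal and clinically significant: Abnormal.
- Normal and clinically significant only: Abnormal if the word covers both abnormal levels; unclassified if it means the middle level alone.

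On neither reading does the output separate subjects who were ever clinically significant.

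**2. Can the by-visit rows supply the count?** Inputs:
- SAP Table 2, footnote j: "ECGs will be conducted every 12 weeks up to Week 96 (ie, Weeks 12, 24, 36, 48, 60, 72, 84, and 96", which is 8 ECGs.
- The same footnote: "every 24 weeks thereafter (ie, Weeks 120 and 144) during the treatment period", which is 2 more.
- Protocol 11.3.7: 1 at the end-of-study visit. Total 8 + 2 + 1 = 11 scheduled post-baseline ECGs at most.
- SAP 3.5: "Approximately 200 subjects will be enrolled", so N = 200.

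Let c_v be the number of subjects with a clinically significant ECG at time point v. The number ever affected lies between max(c_v), if the same subjects recur, and min(N, sum of c_v), if they are all different.
- Assumed c_v = 1 throughout: from 1 to 11 × 1 = 11 subjects, or 1/200 = 0.5% to 11/200 = 5.5%.
- Assumed c_v = 2 throughout: from 2 to 11 × 2 = 22 subjects, or 1.0% to 11.0%.

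The by-visit counts bound the subject count but do not fix it.

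**3. How far could the two-level row mask the category?** Let q be the chance that an ECG is clinically significant and p the chance that it is abnormal but not significant. Both are assumed, with ECGs independent and all 11 obtained.
- Ever clinically significant: 1 − (1 − q)^11. With q = 0.005, 1 − 0.995^11 = 5.4%.
- Row shows 'Abnormal' (broad reading): 1 − (1 − p − q)^11.
  - p = 0.05: 1 − 0.945^11 = 46.3%
  - p = 0.10: 1 − 0.895^11 = 70.5%
  - p = 0.30: 1 − 0.695^11 = 98.2%

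These figures show the mechanism only. Findings that persist within a subject would generally lower them, as would early withdrawal.

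**4. Compare with the SAP's other worst-case rules.** QTcF keeps all its categories at worst post-baseline (9.3). Laboratory shifts go to the worst post-baseline grade (9.2.1). Liver tests count each subject once per threshold, on the worst case (9.2.2). Among these summaries, ECG interpretation is the one whose levels are collapsed, and the SAP gives no reason.

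**The case against.** Much of the case on the other side stands.

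- A reader might infer that the SAP departs from the protocol. It does not: the by-visit display keeps all three levels and so meets the synopsis request, and Protocol 14.3.5 asks for a summary without specifying a count of subjects ever affected.
- A reader might infer that there is no other subject-level ECG result. There is: Table 14.3.5.3 gives numbers of subjects by QTcF category, with a worst post-baseline result. It covers interval prolongation, however, and not morphology or the overall interpretation.
- A reader might infer that clinically significant ECGs are hidden. They are not: Protocol 13.9.2 makes clinically significant ECG changes from baseline reportable as adverse events, SAP 9.1 tabulates these chiefly by subject counts, and Listing 16.2.14 shows each subject's ECG results. But the adverse event tables are by preferred term and do not total subjects by ECG interpretation, and a listing allows a hand count without being a summary.
- The two-level wording may be loose drafting. Display specifications are in a separate document (SAP 12.2), so the actual table layout cannot be seen. That is fair, but the SAP is where the derivation is defined, and as written it has two levels.
- SAP 5.7.12 assigns unscheduled visits to analysis windows, and the worst-case rule does not exclude unscheduled ECGs. They may therefore already count; the SAP says so explicitly only for the QTcF table.

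It is also true that a three-level row would include abnormalities already present at baseline, so it would not be a treatment-emergent count.

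**Conclusion.** The point holds, at a modest size. As SAP 9.3 and Table 7 stand, one subject-level summary is missing: the number of subjects ever interpreted as abnormal clinically significant after baseline. The by-visit rows cannot replace it, and the rule leaves one type of subject history unclassified on a literal reading. This conclusion rests on the text of the rule and the list of displays, not on assumed rates.

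The masking percentages should not be quoted as expected results. A reader might take a figure such as 46% as a forecast for this trial, but the documents give no ECG abnormality rates, and the calculation also assumes independence and full follow-up.

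The study is open-label and uncontrolled, and SAP 3.3 puts estimation above hypothesis testing. The change completes the description of a primary endpoint component and affects no test. It is a free improvement.

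**What to change.** In SAP 9.3, define worst post-baseline ECG interpretation at three ordered levels: abnormal clinically significant if any post-baseline ECG was so interpreted; otherwise abnormal if any was abnormal; otherwise normal. Each subject with post-baseline ECG data then falls in exactly one level, and the missing count is read directly from Table 14.3.5.2. State also that unscheduled post-baseline ECGs count toward this row, as they do in the QTcF table. This matters because Protocol 13.5 calls for a repeat ECG after large QTcF values or changes.

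The cost is a revised SAP sentence and one derivation. The interpretation is already planned for display at three levels, so no new data, visits or tables are needed.
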